6.4. Primary Objective

The primary endpoint is a composite of cardiac death and myocardial infarction (MI) at one year for a one-month clear population [timeframe: one month to one year].

6.4.1. Hypothesis

The primary endpoint of the study will be compared to a pre-specified PG of 9.7%. The study hypotheses are:

$$H_0: \pi \geq 9.7\%$$

$$H_A: \pi < 9.7\%$$

where π denotes the binary rate of cardiac death and myocardial infarction at one year in a one-month clear population [timeframe: one month to one year]. This one-sided test will be carried out at the 0.025 significance level using the binomial exact test.

6.4.2. Primary Endpoint Definition

The primary endpoint is the binary rate of the composite event rate of cardiac death, and myocardial infarction at one-year post-procedure in a one-month clear population. The numerator will be the number of one-month clear subjects who have cardiac death or myocardial infarction, on or before one-year post-procedure (365 days). The denominator will be the number of one-month clear subjects who either have CEC events on or before one year, or have latest date of all follow-up visits, assessments, or events on or after the lower window of one year follow up.

In addition, the KM event rates at 1 month, 2 months, 6 months, 1 year, and 2 years, as well as the KM plot will be provided.

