4.2. Endpoints

4.2.1. Primary Endpoint

Composite of cardiac death and myocardial infarction at one year for a one-month clear population [time frame: one month to one year]

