12.1.2. Hypothesis

Based on historical short DAPT studies with high-bleeding risk patient populations (LEADERS FREE, ZEUS, and SENIOR), the weighted average of cardiac death and myocardial infarction at one year was 9.6%. As disproportionately higher rates of STEMI, unstable angina, and multi-vessel disease were identified in the ZEUS study population which could have led to a higher rate of cardiac death, the ZEUS rate was revised. Similarly, the SENIOR rate contribution was derived from the published rates based on subjects with planned one-month DAPT use.

Approximately 3% of CD/MI events occurred in LEADERS FREE study at 30 days. To account for a “one-month clear” population, the weighted CD/MI rate at 12 months will be discounted by 3%, resulting in an average rate of 6.6%. In addition, to account for the 3% population that will also be removed from the denominator of the rates, the expected CD/MI rate between 30 days and one year is more accurately represented as 6.8%.

The performance goal (9.7%) incorporated a clinically acceptable margin of 2.9% to the expected rate.

In defining a “one-month clear” population, an attrition rate of 20% will be applied to account subjects who interrupted or discontinued DAPT (greater than 3 cumulative days) within the first one month of procedure, who were excluded due to events that would prohibit them from discontinuing DAPT beyond one month, who failed to transition from DAPT to SAPT one month after procedure, and who were lost to follow-up. Peri-procedural MIs will not exclude the patient from being considered as “one month clear”. For the secondary endpoints like TLF, all available biomarkers (including peri-procedural) will be forwarded to the CEC to be used towards the adjudication of events.

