5.1. Sample Size for Primary Objective

Based on historical short DAPT studies with high-bleeding risk patient populations (LEADERS FREE, ZEUS, and SENIOR)^{1,2,3,4,5} the weighted average of cardiac death and myocardial infarction at one year was 9.6%. As disproportionately higher rates of STEMI, unstable angina, and multi-vessel disease were identified in the ZEUS study population which could have led to a higher rate of cardiac death, the ZEUS rate was revised. Similarly, the SENIOR rate contribution was derived from the published rates based on subjects with planned one-month DAPT use.

Approximately 3% of CD/MI events occurred in LEADERS FREE study at 30 days. To account for a “one-month clear” population, the weighted CD/MI rate at 12 months will be discounted by 3%, resulting in an average rate of 6.6%. In addition, to account for the 3% population that will also be removed from the denominator of the rates, the expected CD/MI rate between 30 days and one year is more accurately represented as 6.8%.

The performance goal (9.7%) incorporated a clinically acceptable margin of 2.9% to the expected rate.

In defining a “one-month clear” population, an attrition rate of 20% will be applied to account subjects who interrupted or discontinued DAPT (greater than 3 cumulative days) within the first one month of procedure, who were excluded due to events that would prohibit them from discontinuing DAPT beyond one month, who failed to transition from DAPT to single antiplatelet therapy (SAPT) one month after procedure, and who were lost to follow-up. Peri-procedural MIs will not exclude the patient from being considered as “one month clear”. For the secondary endpoints like TLF, all available biomarkers (including peri-procedural) will be forwarded to the CEC to be used towards the adjudication of events.

Assuming a one-sided alpha level of 0.025 and a true event rate of 6.8%, an effective sample size of 1360 subjects will yield a greater than 97% power to reject the null hypothesis. Assuming a 20% attrition rate, a total sample size of 1700 subjects will be needed.

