6.1. Analysis Populations

Per the CIP, subjects will be considered enrolled into the trial after the following criteria have been met:

1. The signed and dated informed consent has been obtained
2. The patient and target vessel(s)/lesion(s) have met all of the inclusion and none of the exclusion criteria

Revision 4.0

3. The study stent is introduced into the guide catheter

Intent-to-Treat (ITT): All enrolled subjects. Time zero begins at the date of the index procedure.

As Treated (AT): All ITT subjects who received the Resolute ONYX stent only. Time zero begins at the date of the index procedure.

One-month Clear: All subjects who meet all of the following criteria:

- [REDACTED]
- [REDACTED]
- [REDACTED]

[REDACTED]

[REDACTED]

Event-free is defined as that a subject must not have myocardial infarction (MI) (excluding peri-procedural MIs), repeat coronary revascularization, stroke, stent thrombosis (ARC definite/probable), and death. [REDACTED]

[REDACTED]

As Treated and Intent-to-Treat for one-month clear are:

- As Treated Set for One-month Clear: All AT subjects who are in the one-month clear population. This is the primary cohort for the primary endpoint analysis.
- Intent-to-Treat Set for One-month Clear: All ITT subjects who are in the one-month clear population.

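### The primary endpoint counting rule in SAP 6.4.2 omits the one-month lower bound, so read literally it counts peri-procedural MIs of subjects kept in the one-month clear cohort

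*SAP*

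**What the plan says.** The endpoint and the tested parameter both carry a two-sided window. SAP 6.4 defines the composite of cardiac death and myocardial "infarction (MI) at one year for a one-month clear population [timeframe: one month to one year". SAP 6.4.1 defines the tested rate "at one year in a one-month clear population [timeframe: one month to one year". Protocol 4.2.1 agrees: "at one year for a one-month clear population [time frame: one month to one year". SAP 3.1 and Protocol 12.1, 12.1.1 and 12.4 give the same window.

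SAP 6.4.2 then says how subjects are counted: "The numerator will be the number of one-month clear subjects who have cardiac death or myocardial infarction, on or before one-year post-procedure (365 days". Its denominator admits one-month clear subjects with any CEC event up to one year, or with follow-up reaching the lower one-year window. SAP 6.4.5 uses the same CEC-event clause to decide who has complete data. None of these clauses has a lower bound, and SAP 6.1 sets time zero at the index procedure.

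The cohort keeps some subjects with an early MI. SAP 6.1 says that an event-free subject "must not have myocardial infarction (MI) (excluding peri-procedural MIs"). SAP 5.1 says "Peri-procedural MIs will not exclude the patient from being considered as" one-month clear, and Protocol 12.1.2 says the same. SAP 6.4.3 takes cardiac deaths and MIs from the CEC adjudication form.

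**The concern.** In a cohort defined as free of early events, a missing lower bound would normally be harmless, because there would be nothing before one month to count. Here the plan makes an exception for peri-procedural MI, so the omission has content. A programmer who applies the 6.4.2 sentence as written would count a procedural MI found on the CEC form as a primary event. A validator who applies the bracketed window in 6.4.1 would not.

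The goal does not allow for such events. SAP 5.1 removes first-month events from the historical rate and states that "the expected CD/MI rate between 30 days and one year is more accurately represented as 6.8" percent; the 9.7% goal is that figure plus 2.9 points. A numerator that includes procedural MIs would be compared with a benchmark built without first-month events. What is at stake is power for the only hypothesis test and the accuracy of the reported primary rate.

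**Working it through.** **Inputs from the documents** (SAP 5.1, 6.4.1, 6.4.3): goal 9.7%, expected rate 6.8%, one-sided alpha 0.025, exact binomial test, effective sample size 1360, attrition 20%, total 1700, stated power above 97%.

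**Reproducing the plan's figures**

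- Expected rate: (9.6% − 3%) / (1 − 0.03) = 6.80%. Goal: 6.8% + 2.9% = 9.7%. Total: 1360 / (1 − 0.20) = 1700.
- Success limit: the largest c with P(X ≤ c | 1360, 0.097) ≤ 0.025. This is c = 110 (probability 0.0227; c = 111 gives 0.0284).
- The confidence-interval rule in SAP 6.4.3 agrees: the exact upper 95% limit is 9.67% at 110 events and 9.75% at 111.
- Power: P(X ≤ 110 | 1360, 0.068) = 0.971, so the stated figure reproduces.
- Expected events: 1360 × 0.068 = 92.5. The room before the expected count passes the limit is 110 − 92.5 = 17.5 subjects, or 17.5 / 1360 = 1.3% of the cohort.

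**Effect of the literal numerator.** Let m be the share of the one-month clear cohort with a peri-procedural MI. The documents give no value, so m is an assumption, taken as independent of later events. The counted rate is p = m + (1 − m) × 0.068, and power is P(X ≤ limit | n, p). The last column adds an assumed 100 Japanese subjects at 20% attrition: n = 1360 + 0.8 × 100 = 1440, limit 117.

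| Assumed m | Subjects with procedural MI (of 1360) | Counted rate | Power, n = 1360 | Power, n = 1440 |
|---|---|---|---|---|
| 0 | 0 | 6.80% | 97.1% | 97.8% |
| 0.25% | 3.4 | 7.03% | 94.0% | 95.0% |
| 0.5% | 6.8 | 7.27% | 88.8% | 90.3% |
| 1% | 13.6 | 7.73% | 71.0% | 73.1% |

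**Direction.** If the true rate from one month to one year equals the goal, the counted rate is m + (1 − m) × 0.097. With n = 1360 the chance of success is 2.3% at m = 0, 0.6% at m = 0.5% and 0.1% at m = 1%. Literal counting makes success harder.

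**Denominator.** If only the numerator is given a lower bound, a subject whose sole CEC event is early and who is then lost still enters the denominator, as complete and event-free. With an assumed 10 such subjects, the success limit is 110 of 1360 instead of 109 of 1350. This effect is small and favours success.

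**The case against.** The strongest reply is that the window is already fixed. SAP 6.4 and 6.4.1 state it directly above 6.4.2, and reading the numerator sentence alone means ignoring the definition of the tested parameter. Other text points the same way. SAP 6.7 writes both bounds for this population in its publication analyses. SAP 6.5 and 6.5.1 plan no 1-month assessment of the secondary endpoints, which include this same composite, in this cohort. Protocol 12.1.2 links procedural data to other endpoints: "For the secondary endpoints like TLF, all available biomarkers (including peri-procedural) will be forwarded to the CEC". Independent validation of the primary programming (SAP 7) might catch a divergence. Parts of the one-month clear definition in SAP 6.1 are redacted and may bear on the point. The power losses rest on assumed rates.

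Most of this stands as evidence of intent, and the bounded reading is accepted here as the intended one. It does not supply the missing rule. The remark about biomarkers does not say what the primary numerator counts, and no visible text excludes peri-procedural MIs from it. Section 6.4.2 also asks for a 1-month Kaplan-Meier rate of this endpoint, which would be essentially zero once the bound applies, so the section is ambiguous even on its own terms. Validation can expose a disagreement but cannot settle it if the SAP does not. The redaction limits the claim to the visible wording of 6.4.2 and 6.4.5; the numerator sentence itself is not redacted.

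**Conclusion.** The concern holds. The only visible counting rule for the sole hypothesis test does not match the endpoint it implements, and the events affected are the peri-procedural MIs that the plan deliberately keeps in the cohort. Followed exactly, the rule would reduce power from 97.1% to between 94.0% and 71.0% at assumed peri-procedural MI rates of 0.25% to 1%, with slightly smaller losses if Japanese subjects are added. These figures are illustrative, since the documents give no such rate. The error is conservative and cannot produce a false success. It should be fixed before analysis, because it decides which events enter the primary result.

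**What to change.** In the SAP 6.4.2 numerator, count cardiac death or MI with onset after the end of the subject's one-month clear period and no later than day 365. Add a sentence saying that peri-procedural MIs, whether from the index or a planned staged procedure, are not primary endpoint events.

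Tie the bound to the end of the clear period, which Protocol 8.8 extends after a planned staged procedure, and not to a fixed day 30 from index. Staging is allowed up to day 30 and biomarkers are drawn 18 to 24 hours later (Protocol 8.1, Table 2), so a staged peri-procedural MI could be dated day 31. Other deaths and MIs within the clear period already remove the subject from the cohort, so in effect this bound excludes only procedural MIs.

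Apply the same lower bound to the CEC-event clause in the 6.4.2 denominator and in 6.4.5. The 1-month Kaplan-Meier line can stay; it will be close to zero.

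Cost: one clause and one sentence in 6.4.2 and one phrase in 6.4.5. No new data and no protocol change are needed.

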12.10. Missing Data

Deviations from original statistical plan will be avoided, and every effort will be undertaken to minimize missing data. In time-to-event outcomes, dropouts will be censored at the time of discontinuation, consistent with the Kaplan-Meier approach. Unless otherwise specified, no statistical techniques will be used to impute missing data for continuous or categorical outcomes. The number of subjects included in each analysis will be reported so that the reader can assess the potential impact of missing data. Further details are provided in the Statistical Analysis Plan.

13. Economic Analysis

Economic analysis of Resolute Onyx stent in specific study centers may be assessed to determine the relative cost effectiveness after treatment including procedural cost estimated from the viewpoint of the hospital including quality of life instruments. Analysis may include medical costs, procedural aspects of the study such as the use of pre- and post- dilatation, the number of DES attempted to be used, length of stay and any other ancillary devices utilized. Additional details will be listed in the statistical analyses plan.

Access to health economic source documents at each center, if needed, should be made available to the Sponsor in order to enable collection of relevant clinical and cost data.

14. Ethics

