6.4.5. Missing Data Analysis

Every effort will be undertaken to minimize missing data. One-month clear AT subjects with primary endpoint events, or with CEC events on or before one year, or with any follow-up visits, assessments, or events on or after the lower window of one year follow up will be considered to have complete data for the purposes of this analysis. If outcome data are missing, to assess the potential impact of missing data, a sensitivity analysis will be conducted which will include a complete case (including only subjects whose status is known at one year), a best-case (assume missing Resolute Onyx subjects are event free at one year), a worst-case (assume missing Resolute Onyx subjects have event at one year), and a tipping point analysis if the conclusion is changed in the worst-case analysis.

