6.5.1. Data Collection and Analysis Methods

The data on the CEC adjudication form will be used in the analysis. For secondary endpoints, event rates/success rates, and 95% two-sided confidence interval will be provided. The time-sensitive nature of any response variable will be displayed by using a Kaplan-Meier plot.

The primary analysis for secondary endpoints at follow-up time points (2, 6 months, 1 and 2 years) will be performed for AT one-month clear population, except that the acute success. The secondary analysis for secondary endpoints (except acute success) at all follow-up time points (1, 2, 6 months, 1 and 2 years) will be performed based on the AT set.

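### A subject lost to follow-up after a non-fatal bleed counts as a complete non-event in the primary analysis and bypasses the worst-case and tipping-point analyses

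*SAP*

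**What the plan says.** SAP 6.4.2 sets the numerator first: "The numerator will be the number of one-month clear subjects who have cardiac death or myocardial infarction, on or before one-year post-procedure (365 days"). For the denominator it gives two routes. The first is "The denominator will be the number of one-month clear subjects who either have CEC events on or before one year". The second is to "or have latest date of all follow-up visits, assessments, or events on or after the lower window of one year follow up". Under SAP Appendix II that lower limit is 30 days before the one-year anniversary.

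SAP 6.4.5 uses the same idea to decide who has complete data, and names three routes: "One-month clear AT subjects with primary endpoint events, or with CEC events on or before one year, or with any follow-up visits", and so on for contacts at or after the lower window. Sensitivity analyses follow only for missing outcome data. They are "a complete case (including only subjects whose status is known at one year"), a best case, a worst case that counts missing subjects as events, and "a tipping point analysis if the conclusion is changed in the worst-case analysis".

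The visible SAP text does not define a CEC event. Protocol 8.12 has the CEC adjudicate events possibly related to the study endpoints, and SAP 6.5.1 opens with: "The data on the CEC adjudication form will be used in the analysis. For secondary endpoints". Those secondary endpoints include stroke, all revascularization, stent thrombosis and every BARC grade of bleeding.

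**The concern.** Having had an adjudicated event does not show that a subject was followed for a year. For death it settles the subject's status, and for MI it settles the endpoint. For a non-fatal bleed, stroke or revascularization it settles neither. A subject who bleeds on day 40 and is lost on day 50 has more than ten unobserved months, yet enters the confirmatory test as event-free to day 365.

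The clause gives no lower date. Bleeding is not on the visible list of events that remove a subject from the one-month clear set (SAP 6.1), so a first-month bleed would appear to qualify as well.

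The main damage is to the missing-data check. The worst case exists to show whether unobserved outcomes could overturn the result, and these subjects are left out of it. Because the tipping-point analysis runs only if the worst case changes the conclusion, a pass produced by the completeness rule also removes that analysis. The error runs one way: it can only make the result look better. This is also a high-bleeding-risk trial that collects all bleeding, and Protocol 9.1 itself describes major bleeding as correlated with adverse events.

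**Working it through.** **Reading of the term.** SAP 6.4.5 lists primary endpoint events and CEC events as separate routes, so the second must be wider than the first. Protocol 8.12 and SAP 6.5.1 indicate what the wider class contains.

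**Consistency.** The same subject is treated three ways. SAP 6.4.2 and the completeness sentence of 6.4.5 count the subject as complete. The complete case in 6.4.5 asks for known status at one year, which the subject lacks. In the Kaplan-Meier estimate, under Protocol 12.10, "dropouts will be censored at the time of discontinuation, consistent with the Kaplan-Meier approach".

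**Inputs from the documents.** Goal 9.7%, one-sided 0.025, exact binomial (SAP 6.4.1). Effective size 1360, true rate 6.8%, power above 97% (SAP 5.1).

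**Assumed inputs.** The share of the 1360 lost before the one-year window, l, and the share of those with an earlier non-primary, non-fatal CEC event, h. SAP 5.1 gives only a 20% attrition figure that mixes loss with other reasons.

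**The plan's own figure.** With n = 1360 and p = 0.097, P(X ≤ 110) = 0.0227 and P(X ≤ 111) = 0.0284, so the study succeeds with 110 events or fewer. At p = 0.068, P(X ≤ 110) = 0.971, which agrees with the stated power.

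**Formulas.** Lost L = 1360·l. Affected H = L·h. Recognised as missing V = L − H. Expected observed events E = 0.068·(1360 − L).

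- Primary rate: E/(1360 − L + H) under the SAP rule; E/(1360 − L) under the corrected rule.
- Worst-case count, against the limit of 110: E + V under the SAP rule; E + V + H under the corrected rule.

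**Number affected.** From 1360 × 0.02 × 0.10 = 2.7 to 1360 × 0.06 × 0.30 = 24.5.

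**Primary rate.** At l = 2%, h = 10%: 6.786% against 6.800%. At l = 6%, h = 30%: 6.672% against 6.800%. The difference is 0.01 to 0.13 points.

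**Expected worst-case count.**

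| l | h | SAP rule | Corrected |
|---|---|---|---|
| 1.5% | 20% | 91.1 + 16.3 = 107.4 | 111.5 |
| 2% | 10% | 115.1 | 117.8 |
| 2% | 30% | 90.6 + 19.0 = 109.7 | 117.8 |
| 4% | 20% | 132.3 | 143.2 |

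The first and third rows fall on opposite sides of 110. At 2% loss with h = 10% or 20%, and at 3% loss or more, the expected count exceeds 110 under both rules.

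**Probability that the worst-case verdict differs.** This is P(110 − V − H < X ≤ 110 − V), with X, the observed events, ~ Bin(1360 − L, 0.068) and counts rounded:

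| l | h = 10% | h = 20% | h = 30% |
|---|---|---|---|
| 1% | 0.035 | 0.098 | 0.126 |
| 2% | 0.110 | 0.193 | 0.323 |
| 3% | 0.024 | 0.078 | 0.175 |
| 4% | 0.001 | 0.008 | 0.033 |

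**Cross-check without l and h.** With 92 events among 1360 (0.068 × 1360 = 92.5) and no other missing subjects, adding 18 affected subjects as events gives 110 and an upper 95% limit of 9.67%, a pass. Adding 19 (1.4% of 1360) gives 111 and 9.75%, a fail. Under the SAP rule none is added and the limit stays at 8.23%.

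**The case against.** The term is undefined in what can be read: parts of SAP 6.1 are redacted, and Protocol 11.1 leaves the CEC's procedures to a separate charter. Protocol section 5 sets the minimum scope as deaths and safety-endpoint events, so the extra class might be mainly non-cardiac deaths, whose status is known. This stands as a limit on certainty. The wider reading remains the natural one, because Protocol 8.12 and SAP 6.5.1 both point to it.

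The complete-case wording could be read to exclude these subjects, and the Kaplan-Meier rate censors them. Both points are fair. But the complete-case wording conflicts with the sentence before it, and Kaplan-Meier is not the confirmatory test. A binary rate and a Kaplan-Meier rate may also differ by design, so that difference alone proves nothing.

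The missing lower date can be answered by the endpoint's one-month to one-year time frame, which the numerator also relies on. The first-month example is therefore arguable; the day-40 example is not affected.

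The size rests on assumed rates. The count of 109.7 is an expectation just under the limit and uses the highest assumed share; the probability of passing there is about 54% under the SAP rule, against 22% corrected. At 4% loss or more the worst case nearly always fails either way. Running a tipping-point analysis only after a failed worst case is ordinary practice, provided the worst case includes everyone whose status is unknown. Protocol 8.19 asks for repeated contact attempts and recommends death-database checks, which reduces missed deaths but not missed MIs.

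**Conclusion.** The concern holds. As worded, SAP 6.4.2 and 6.4.5 classify some incomplete follow-up as complete and event-free. Subjects lost with no CEC event are handled correctly: they leave the denominator and go to the sensitivity analyses.

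The effect on the primary rate is small over the assumed range, and no type I error inflation is claimed. The practical effect is on the worst-case check, mostly when loss is near 1% to 2%; at 3% loss the verdict differs with probability 2% to 18%, and at 4% with 0.1% to 3%. These figures assume a true rate of 6.8%, 1360 one-month clear subjects, the stated ranges for loss and for earlier events, and the wider reading of a CEC event. The change should be made. Confidence is medium because the term is undefined and the loss rates are not in the documents.

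**What to change.** In SAP 6.4.2 and 6.4.5, replace the CEC-event route with a primary endpoint event or death from any cause, on or before one year. This keeps non-cardiac deaths, whose one-year status is known. Every other subject should need a contact on or after the lower one-year window to be complete. The rest are missing and enter the best-case, worst-case and tipping-point analyses. The completeness sentence and the complete-case definition in 6.4.5 then agree.

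The cost is SAP wording and one derivation flag. Under the assumed ranges about 3 to 24 of 1360 subjects move from complete to missing, the worst-case count rises by the same number, and the primary rate may rise by about 0.1 point. If the sponsor always meant primary events and deaths only, no result changes and the text simply says so.
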